2.2 Secondary objectives

- (1) Determine whether there are differences in low and high shear rate dependent viscosity with treatment by ticagrelor alone and combination aspirin-ticagrelor.
- (2) Investigate the effect of the treatment on peripheral arterial blood flow using pulse volume recordings, ankle brachial index, toe pressures and laser flow Doppler (a new emerging technique capable of measuring the velocity of flow and number of cells in the vessel, providing a normalized measure of microcirculatory flow (velocity of flow x number of cells/backscatter)

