5.2 Subject enrollment and randomization

5.2.1 Procedures for randomization

Study participants will be randomized into 3 groups, and each group will receive each of 3 treatments in the cross-over study. Block randomization will be used to create groups which have equal and balanced sample sizes (i.e. for every block of 6 subjects, two will be enrolled to each arm of the study).

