5.5.2 Doses and treatment regimens

The 3 treatment groups will receive:

1. Group A: Aspirin 81 mg daily and ticagrelor placebo twice daily
2. Group B: Aspirin 81 mg daily and ticagrelor 90 mg twice daily
3. Group C: Aspirin placebo daily and ticagrelor 90 mg twice daily

Each treatment group will receive all 3 of the above treatments in this cross-over study.

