12.1.1 Efficacy analysis set

For the first primary aim, a pre-planned contrast statement (proc mixed) will be used to compare the pooled effect of aspirin-ticagrelor with aspirin. Similarly, for the second primary aim, a contrast statement will be used to compare the pooled effect of ticagrelor monotherapy with aspirin. A one-tailed hypothesis test will be used for each contrast, and a Bonferroni correction will be used to control family wise error rate; a one-tailed significance level of 0.025 will be used for both contrasts. The above contrasts shall act effectively as a paired t-test on the dependent variable blood viscosity.

For the first secondary aim, an effect size will be calculated to estimate the standardized difference between ticagrelor monotherapy and combination aspirin-ticagrelor. Low-dose aspirin was previously reported to have no significant effect on blood viscosity. The present study is powered to detect differences between ticagrelor and low-dose aspirin—not between ticagrelor monotherapy and combination aspirin-ticagrelor. An effect size corresponding to a dependent t-test will be calculated to determine the practical magnitude of the difference in blood viscosity measures between the two ticagrelor arms of the study.

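### The comparison of ticagrelor alone with aspirin-ticagrelor is planned only as a standardised effect size; it should be reported as a difference in cP with a confidence interval.

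*Combined protocol and SAP*

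**What the plan says.** Section 2.2, objective (1), poses a question to be decided: "Determine whether there are differences in low and high shear rate dependent viscosity with treatment by ticagrelor alone and combination aspirin-ticagrelor". Section 12.3 repeats that the two ticagrelor regimens will be compared as a secondary aim, but gives no method or target difference.

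The method is in section 12.1.1: "For the first secondary aim, an effect size will be calculated to estimate the standardized difference between ticagrelor monotherapy and combination aspirin-ticagrelor". Its purpose follows: "An effect size corresponding to a dependent t-test will be calculated to determine the practical magnitude of the difference in blood viscosity measures". The section does not define the denominator, name the shear rate, or plan an interval or test for this pair.

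Between these two sentences stand a premise and a reason. The premise is "Low-dose aspirin was previously reported to have no significant effect on blood viscosity". The reason is that "The present study is powered to detect differences between ticagrelor and low-dose aspirin" and "not between ticagrelor monotherapy and combination aspirin-ticagrelor".

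The two primary aims are handled differently. Each gets a pre-planned PROC MIXED contrast at one-sided 0.025. Section 12.1 adds tests of treatment, period and sequence effects at 0.05. That treatment test covers all three regimens together and does not isolate this pair.

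**The concern.** The objective asks whether two regimens differ, and the planned output is a single standardised number. Such a number has two weaknesses here.

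- **Magnitude.** Practical magnitude is naturally read in cP, the unit in which section 12.3 plans the trial. A paired effect size in its usual form divides by the SD of the within-patient differences, so it depends on the within-patient correlation as well as on the size of the difference.
- **Uncertainty.** Without an interval, the reader cannot see which differences the data exclude.

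At stake is the one comparison that shows whether adding aspirin to ticagrelor changes viscosity. The trial will hold the data to estimate it, but as planned the report would not state the estimate in a usable form.

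**Working it through.** **Inputs from the documents**
- SD of low-shear (5 s⁻¹) viscosity: 2.42 cP (section 12.3, taken from the baseline control group of an earlier study).
- 72 patients required, 24 per group; 90 randomised (section 12.3).
- Design: "Each treatment group will receive all 3 of the above treatments in this cross-over study" (section 5.5.2). Allocation: "for every block of 6 subjects, two will be enrolled to each arm of the study" (section 5.2.1).

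**Assumptions**
- The documents give no within-patient correlation ρ, so 0, 0.5 and 0.8 are used as a range.
- Variance and correlation are taken as equal across the three treatments.
- The effect-size denominator is taken as the SD of paired differences, because the text does not define it.

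**The plan's own figure.** Section 12.3 sizes only the comparisons with aspirin (2.0 cP, 90% power, 5% type I error). A parallel two-sample normal calculation at one-sided 0.05 gives 26 per group, against the stated 24; with 24 the power is 88.8%. That is a loose match, and there is no figure for monotherapy versus combination to reproduce. The 72 is used below only as the number of completers.

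**Step 1: SD of the paired difference.** SD_diff = 2.42 × √(2(1 − ρ)).

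**Step 2: standard error and interval.** SE = SD_diff / √72. The 95% half-width is t(0.975, 71) × SE, with t = 1.994.

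**Step 3: how 1.0 cP would appear.** Effect size = 1.0 / SD_diff.

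| ρ (assumed) | SD_diff (cP) | SE (cP) | 95% half-width (cP) | Effect size for 1.0 cP |
|---|---|---|---|---|
| 0 | 3.42 | 0.403 | 0.80 | 0.29 |
| 0.5 | 2.42 | 0.285 | 0.57 | 0.41 |
| 0.8 | 1.53 | 0.180 | 0.36 | 0.65 |

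If the denominator were instead the single-treatment SD, 1.0 cP would read as 1.0 / 2.42 = 0.41 at every ρ. The undefined denominator therefore matters.

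**Step 4: does this contrast have the precision of the primary ones?** The generalised least squares variance was computed for the three sequences of section 3.1, with 24 completers each and period and sequence in the model. Combination versus aspirin, monotherapy versus aspirin, and monotherapy versus combination all have the same SE: 0.403, 0.285 and 0.180 cP at the three correlations. These equal the paired values above.

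**Step 5: what a bare effect size leaves open.** Take an observed paired effect size of 0.20 with 72 pairs. Its approximate SE is √(1/72 + 0.20²/(2 × 72)) = 0.119, so the 95% CI is 0.20 ± 1.96 × 0.119, or −0.03 to 0.43. In cP the same 0.20 is 0.68, 0.48 or 0.31 (0.20 × SD_diff) at the three correlations. Neither the range nor the size in cP can be read from the number 0.20.

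These figures apply to low shear. The documents give no SD at 300 s⁻¹, so the precision there cannot be computed.

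**The case against.** **The power statement is true.** A reader might infer that the plan wrongly claims less precision for this contrast. It does not: it says only that the study was not powered for it, and section 12.3 indeed sizes only the aspirin comparisons. The adjacent remark about low-dose aspirin suggests that a small difference is expected, and power depends on that difference. As an illustration, with 72 pairs at two-sided 0.05 and correlations of 0 and 0.5, power is 69% and 93% for 1.0 cP, but 23% and 41% for 0.5 cP. The objection stands, and the sentence can stay. It does not justify leaving out an interval, which matters more when the expected difference is small.

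**The 2.0 cP figure is no yardstick here.** It is tempting to call the half-widths narrow against 2.0 cP. That value was interpolated from clopidogrel data for the comparisons with aspirin, and nothing in the documents ties it to adding aspirin to ticagrelor.

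**The effect size is not uninformative.** If the denominator is the SD of differences, multiplying by √N returns the t statistic, and a test or interval could be derived. That is so, but neither is pre-specified, and the denominator is not stated.

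**Period effects.** A reader might infer that a paired statistic is biased because it lacks period terms. In the section 3.1 sequences, combination minus monotherapy carries period effects p2 − p3, p1 − p2 and p3 − p1 in Groups A, B and C. These sum to zero, so they cancel in the mean when the sequences have equal numbers of completers. What remains is some inflation of the SD, and possible bias if dropout is unequal.

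**Equivalence.** No passage plans to conclude equivalence from a small effect size, and the power statement itself cautions against it.

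**Conclusion.** The point holds as a mismatch between objective and analysis. Section 2.2(1) asks whether the regimens differ at both shear rates; section 12.1.1 offers a standardised number with an undefined denominator, and no cP estimate, interval or test for this pair.

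The size of the problem is the ambiguity of that number: 1.0 cP may read as anything from 0.29 to 0.65. What the design can offer instead is an interval of about ±0.80 to ±0.36 cP at low shear. Both ranges rest on an SD of 2.42 cP and assumed correlations from 0 to 0.8. The first also assumes the SD of differences as denominator. The second also assumes 72 completers and equal variances and correlations across treatments; dropout that differs between periods would make the three contrasts less alike.

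The documents do not support calling the power statement wrong, or reading the gap as a threat to the primary results. It concerns a secondary objective only.

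**What to change.** In section 12.1.1:

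1. Add a third ESTIMATE statement, monotherapy versus combination, to the same PROC MIXED model as the primary contrasts. Report the difference in cP with a two-sided 95% CI at 5 s⁻¹ and at 300 s⁻¹.
2. Keep the effect size as a supplement, and state its denominator and the shear rates at which it is computed.
3. Keep the statement that the study was not powered for this contrast, and add the expected precision beside it, with the assumed correlation named.

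The cost is one line of code and a few sentences of text. No new data are needed, and because the estimate is secondary, the two Bonferroni-controlled primary tests are unchanged.

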12.1.2 Safety analysis set

Not applicable.

12.2 Methods of statistical analyses

All statistical analyses will be performed using SAS (Statistical Analyses System, Cary, NC). Our statistical considerations assume that there is no carryover effect between treatments. In order to verify this assumption, dependent t-tests will be conducted to compare day 1 and week 6 measures of blood viscosity, and dependent t-tests will be conducted to compare day 1 and week 12 measures for blood viscosity.

12.2.1 Interim analyses

Not applicable.

12.3 Determination of sample size

The scanning capillary viscometer that will be used in the proposed study was employed in an earlier study of 47 patients with hyperhomocysteinemia in addition to stable CVD or high CVD risk factors based on a Framingham score of >20% [13]. In this prior CVD population, mean blood viscosity levels at a low shear rate of 5 s^{-1} were reported to be $9.98 \pm 2.42\text{ cP}$ in the control group at baseline. A standard deviation of 2.42 cP for low-shear (5 s^{-1}) blood viscosity was used throughout our sample size calculations. Separately, treatment by clopidogrel 75 mg daily for 3 weeks was reported to reduce viscosity levels by 0.6 cP and 5.0 cP at shear rates of 94.5 s^{-1} and 0.94 s^{-1} , respectively [12]. Using this data, blood viscosity reduction of 2.0 cP by clopidogrel was interpolated for a shear rate of 5 s^{-1} . The present cross-over design study is powered to detect a 2.0 cP difference in low-shear blood viscosity at a shear rate of 5 s^{-1} , relative to aspirin 81 mg, with 90% power using a type I error rate of 5%. Combination aspirin-ticagrelor and low-dose aspirin control will be compared, and separately, ticagrelor monotherapy and low-dose aspirin control will be compared. This requires 72 patients (24 patients in each of 3 groups). Accounting for dropout, we will randomize 90 patients, or 30 patients in each of 3 arms. The effects of combination aspirin-ticagrelor and ticagrelor monotherapy will also be compared as a secondary aim.

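### The planned paired analysis does not need 72 patients for 90% power at 2.0 cP; on the plan's own inputs it needs 33 completers or fewer at any non-negative within-patient correlation

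*Combined protocol and SAP*

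**What the plan says.** Section 12.3 takes a low-shear (5 s⁻¹) SD of 2.42 cP from an earlier cardiovascular study, where it was observed "in the control group at baseline", and says this SD for "blood viscosity was used throughout our sample size calculations". The target is a 2.0 cP difference from aspirin 81 mg, "with 90% power using a type I error rate of 5" percent. The stated result is "This requires 72 patients (24 patients in each of 3 groups"), and then: "Accounting for dropout, we will randomize 90 patients, or 30 patients in each of 3 arms".

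Section 12.1.1 sets out the analysis. Aspirin-ticagrelor and ticagrelor alone are each compared with aspirin by a pre-planned contrast. On the form of the test: "The above contrasts shall act effectively as a paired t-test on the dependent variable blood viscosity". On its level: "a one-tailed significance level of 0.025 will be used for both contrasts". Section 5.5.2 confirms the crossover: "Each treatment group will receive all 3 of the above treatments in this cross-over study".

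**The concern.** The three groups of 24 are treatment sequences, not comparison arms. A patient in any sequence provides a value on aspirin, on aspirin-ticagrelor and on ticagrelor alone, so all 72 completers enter each contrast. A paired comparison with 72 pairs, an SD of 2.42 cP and a 2.0 cP target should have far more than 90% power. Either the sample size was worked out for a different analysis, or an input is missing.

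If the figure is wrong, an ethics reviewer judging how many patients need to be exposed, or a reader interpreting a null result, would take 2.0 cP as the smallest difference the trial can reliably detect. On the plan's inputs the trial can detect a considerably smaller one. Section 12.3 also gives neither a formula nor a within-patient correlation or SD of the difference, so its figure cannot be checked from the text.

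**Working it through.** **Inputs.** Difference 2.0 cP, SD 2.42 cP and power 90% (Section 12.3); paired contrast at one-tailed 0.025 (Section 12.1.1); all patients receive all treatments (Section 5.5.2). The SD comes from one group at baseline, so it is read as the SD of a single measurement and, as Section 12.3 uses one value throughout, taken as equal under both treatments. The within-patient correlation ρ is not in the documents; the values below are assumptions.

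**Formulas.** SD of the paired difference: SDd = SD × √(2(1 − ρ)). Power: noncentral t with n − 1 degrees of freedom and noncentrality 2.0 / (SDd/√n). Normal approximation as a check: n = ((1.960 + 1.282) × SDd / 2.0)².

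**Trying to reproduce 72.** No route consistent with the plan gives it.

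- *Paired test, planned level, ρ = 0.* SDd = 2.42 × √2 = 3.42 cP. The normal approximation gives (3.242 × 3.42 / 2.0)² ≈ 30.8, so 31. The t calculation gives 33 (power 89.3% at 32, 90.2% at 33).
- *Paired test, other levels, ρ = 0.* 27 at one-tailed 0.05; 39 at one-tailed 0.0125.
- *2.42 cP read as the SD of the difference.* 18.
- *Two parallel arms, t-test.* At one-tailed 0.05, 26 per arm are needed, and 24 per arm give 88.0% power. At one-tailed 0.025, 32 per arm are needed, and 24 per arm give 80.0%.
- *Three-group ANOVA with means 0, 2, 2 at 0.05.* 87 in total.

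**Requirement and performance of the planned test** (one-tailed 0.025, SD 2.42 cP):

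| ρ (assumed) | SDd, cP | n for 90% power | Power at n = 72 | Detectable difference at n = 72, 90% power |
|---|---|---|---|---|
| −1 | 4.84 | 64 | 93.3% | 1.87 cP |
| −0.3 | 3.90 | 42 | 99.0% | 1.51 cP |
| 0 | 3.42 | 33 | 99.8% | 1.33 cP |
| 0.3 | 2.86 | 24 | >99.9% | 1.11 cP |
| 0.5 | 2.42 | 18 | >99.9% | 0.94 cP |

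For 72 to be the smallest sufficient n, SDd would have to be about 5.13 to 5.16 cP. With a common SD of 2.42 cP, SDd cannot exceed 2 × 2.42 = 4.84 cP.

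**Sensitivity to the SD.** The SD comes from another population. Section 1.3 cites mean low-shear viscosity 13% to 30% higher in diabetic patients than in controls but gives no SD, so the larger SDs here are assumptions.

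| SD | ρ | n for 90% power | Power for 2.0 cP at n = 72 | Detectable difference at n = 72 |
|---|---|---|---|---|
| 3.15 cP (+30%) | 0 | 54 | 96.4% | 1.72 cP |
| 3.15 cP (+30%) | 0.3 | 39 | 99.4% | 1.44 cP |
| 3.15 cP (+30%) | 0.5 | 28 | >99.9% | 1.22 cP |
| 3.63 cP (+50%) | 0 | 72 | 90.3% | 1.99 cP |

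**The case against.** The main counter-argument is about weight. A trial with 99.8% power still meets a 90% target; type I error and the estimates are untouched; and the remedy changes no patient, visit or test. That stands, and it limits the consequence to a misstated figure.

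Second, there are plausible origins for 72. The paired requirement is 24 at ρ = 0.3 (and also at one-tailed 0.05 with ρ = 0.1), so a total of 24 may have been applied to each sequence and multiplied by three. Alternatively, 24 per arm is close to a parallel-group size at one-tailed 0.05. Both are inferences. Neither makes 72 the requirement, because Section 12.1.1 tests effects pooled over sequences.

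Third, the sidedness and level missing from Section 12.3 are stated in Section 12.1.1. That is so; what is absent from the whole plan is the correlation or the SD of the difference.

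Fourth, the claim that no correlation gives 72 depends on equal SDs and on the planned level. With 2.42 cP on aspirin and about 4.55 cP on ticagrelor at ρ = 0, the requirement would be 72; at one-tailed 0.0125 it would be 72 with ρ near −0.9. Both are arithmetically possible, but the first departs from the single SD in Section 12.3 and the second from the level in Section 12.1.1.

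Finally, the true SD in this population is unknown, and with an SD 50% larger 72 would be about right. This is a good reason not to cut the sample size. It does not make the printed calculation correct.

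**Conclusion.** The concern holds. The stated requirement of 72 for 90% power at 2.0 cP is wrong for the analysis and inputs the plan sets out: it is more than twice the 33 completers needed at ρ = 0, and the gap widens as ρ rises. The conclusion rests on reading 2.42 cP as a single-measurement SD common to the treatments compared, but the alternative reading, as the SD of the difference, moves the requirement further from 72. It does not depend on which correlation is assumed at the planned level.

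This shows that 72 is inconsistent with the plan's inputs, not that 72 is too many for this population. How 72 was obtained cannot be determined from the text. The point should be fixed, but it does not threaten the validity of the trial.

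**What to change.** Keep 72 completers and 90 randomized, and rewrite the power statement in Section 12.3 for the paired analysis. Suggested content:

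> All completers contribute to both low-shear contrasts, each a paired comparison at one-tailed 0.025, with SD of the difference = SD × √(2(1 − ρ)). If the single-measurement SD is 2.42 cP, 72 completers give about 99.8% power for 2.0 cP at ρ = 0 and more at positive ρ, and 90% power for about 1.33, 1.11 or 0.94 cP at ρ = 0, 0.3 or 0.5. If the SD were 30% larger, power for 2.0 cP at ρ = 0 would be about 96%, and the corresponding differences about 1.72, 1.44 or 1.22 cP.

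If the sponsor has data on the within-patient correlation or the SD of the difference, those should replace the assumed values. The text should say that the calculation covers low shear only: Section 2.1 also includes 300 s⁻¹ in the primary objective, and Section 12.3 gives no SD or target difference there. The dropout rate implied by 1 − 72/90 = 20% can be stated in the same edit. The calculation should not be used to reduce the sample size.

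The cost is wording in one section, with no change to patients, visits or analysis.

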12.4 Data monitoring committee

Unless specifically requested by the IRBs at the clinical sites, we will not convene a DMC due to the short-term nature of the trial. If a formal DMC is required, the appropriate costs for the physician's time will be included in a revised budget.

13. IMPORTANT MEDICAL PROCEDURES TO BE FOLLOWED BY THE INVESTIGATOR

13.1 Overdose

If an overdose on an AstraZeneca study drug occurs in the course of the study, then investigators or other site personnel inform appropriate AstraZeneca representatives **within one day**, ie, immediately but no later than **the end of the next business day** of when he or she becomes aware of it.

The designated AstraZeneca representative works with the investigator to ensure that all relevant information is provided to the AstraZeneca Patient Safety data entry site.

13.2 Pregnancy

All outcomes of pregnancy should be reported to AstraZeneca.

13.2.1 Maternal exposure

Not applicable.

13.2.1.1 Paternal exposure

Not applicable.

